down, and flexibility exercises; review the Borg Rating of Perceived Exertion (RPE); set goals with the patient; and answer any questions they might have. The exercise physiologist will then document in the electronic medical record any warning symptoms the participant experienced during physical activity or exercise; recent hospitalizations, important medical appointments, urgent care, or emergency department visits; goals set during phone call; an individualized exercise prescription. Study personnel will then send the individualized exercise prescription to the participant via mail, portal, or email. Recommended aerobic exercises will include arm and/or leg ergometry using a pedal exerciser. Recommended resistance training will include resistance bands. Patients will be encouraged to obtain at least 30 minutes of moderate-intensity physical activity at least five days per week. Gradual increases in the volume of physical activity will be recommended over time. Participants on dialysis will be advised not to exercise after in-center hemodialysis on dialysis days (if applicable). Participants will be asked to log information regarding their exercise sessions on paper, including type, duration, and Borg RPE scale.

During the subsequent weekly phone calls, the exercise physiologist will inquire about any interim symptoms or events, answer any questions regarding the exercise program, review goals set during the previous phone call and what the patient has done to work toward those goals, and set new goals if applicable. During each weekly phone call, the exercise physiologist will review and record information from the patients exercise log and enter it into the patients electronic medical record. Information entered by exercise physiologists into the electronic medical record will also be entered into REDCap by study personnel.

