Participants will be instructed to stop exercising and sit down and rest if they develop any of the following signs: chest tightness, pressure, or pain; severe shortness of breath; light-headedness or dizziness; stomach pain; upset stomach, throwing up or a headache; pulse rate that is not normal for them; extreme fatigue; profuse sweating. They will be advised to seek emergency care (call 911) immediately for chest tightness, pressure, or pain in the chest or severe shortness of breath that does not go away within 3 to 5 minutes. Home-based exercise will be stopped if the study team feels it is no longer safe for the participant to continue exercise. If a participant experiences any of the above symptoms during or after exercising, the principal investigators will be notified. If the principal investigators determine it is no longer safe for the participant to continue the exercise program following discomfort, injury, or a medical emergency during an exercise session, the participant will be withdrawn from the study. Reasons for participant withdrawal will be recorded.

Study measures:

Participants will complete the following Short Physical Performance Battery testing and other study measures at baseline and after completion of the exercise program:

1. Fried Frailty Phenotype: The Fried Frailty Phenotype consists of a gait speed test, a grip strength test, and self-reported measures of physical activity, weight loss, and exhaustion. a. Gait speed test: The time required for the participant to walk a distance of 15 feet at a self-

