3. Kidney Disease Quality of Life Short Form (KDQOL-SF), Version 1.3: Participants will complete this 37-item questionnaire, which consists of questions regarding the patients kidney disease, their quality of life, and demographic characteristics. 4. Actigraph: Participants will be asked to wear an actigraph on their upper extremity for 7 days in a row and mail the device back to us in a prepaid envelope. The actigraph monitoring will be performed both at baseline and after completion of the exercise intervention. 5. Weight: Participants' weight will be measured on a scale.

Demographic and health information: At baseline, participants will be asked to self-report their marital status, employment status, insurance, education, income, smoking history, time on dialysis, dialysis type and location, and dialysis days. If patients do not provide this information, it will be collected from the medical record when possible. Medical information, including body mass index, cause of renal disease, previous kidney transplant, and comorbidities, will be abstracted from the participants' medical record.

Participants will be offered the option of completing questionnaires via Baylor College of Medicine iPAD, on paper, or over the phone. Participants will be able to skip any question that makes them uncomfortable or that they do not want to answer.

If a participant feels unsafe or if the study team member performing the frailty/Short Physical Performance Battery tests feels the participant is unsafe at any point during the frailty/Short Physical Performance Battery tests, the participant will not be asked to complete that measure.

End of Intervention Qualitative Survey:

Following completion of the home-based exercise program, participants will be asked to complete a qualitative/satisfaction survey. Approximately one month after completion of the exercise program, participants will be asked to complete some additional questions via phone or mail to ascertain if they are still exercising.

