A Data Transfer Agreement will be obtained between Mayo Clinic and Baylor College of Medicine so that a limited data set involving subjects from Mayo Clinic can be accessed from Baylor College of Medicine. Mayo Clinic will share the data with Baylor using encrypted email and/or Microsoft Simple Share. The limited dataset that will be shared will include demographics, dates of participation in the exercise intervention, information about the exercise intervention (i.e. duration of study phone calls, participant exercise log), study outcome data (including data from frailty assessments, body composition assessments, accelerometers, and questionnaires), and medical/laboratory information abstracted from the medical record.

Sample Size/Data Analysis

Sample Size

How many subjects (or specimens, or charts) will be used in this study?

Local: 20 Worldwide: 20

Please indicate why you chose the sample size proposed:

This is a pilot study so it doesn't require sample size calculations. However, we chose our recruitment target based on a prior study examining the impact of exercise on frailty parameters which was able to show significant differences with a similar number of study participants.

Data Analysis

Provide a description of your plan for data analysis. State the types of comparisons you plan (e.g. comparison of means, comparison of proportions, regressions, analysis of variance). Which is the PRIMARY comparison/analysis? How will the analyses proposed relate to the primary purposes of your study?

Categorical variables will be summarized as counts and percentages with continuous variables summarized via medians and interquartile ranges. Pre- and post- comparisons will be made using paired, one-sample Wilcoxon signed rank tests for continuous variables and chi-square tests for categorical variables. Differences between groups will be assessed using two-sample Wilcoxon tests for continuous variables and Fisher's exact tests for categorical variables. P-values less than 0.05 will be considered statistically significant. We will make no adjustments in the p-value for multiple hypothesis testing.

Potential Risks/Discomforts

Describe and assess any potential risks/discomforts; (physical, psychological, social, legal, or other) and assess the likelihood and seriousness of such risks:

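### Participants withdrawn for safety after an exercise-session event have no planned post-programme measures, so they drop out of the paired pre/post analysis for a reason that may be linked to outcome

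*Combined protocol and SAP*

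**What the plan says.** The protocol's Exercise Intervention section has two safety sentences. The general one reads "Home-based exercise will be stopped if the study team feels it is no longer safe for the participant to continue exercise". The specific one covers discomfort, injury or a medical emergency during a session: if the principal investigators then judge continuation unsafe, "the participant will be withdrawn from the study". The reason for withdrawal is recorded.

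The Study measures section schedules the Fried phenotype, SPPB, KDQOL-SF, actigraphy and weight as "other study measures at baseline and after completion of the exercise program". Actigraphy timing is repeated separately: "The actigraph monitoring will be performed both at baseline and after completion of the exercise intervention". No early-termination visit is described, and no week-8 visit for people who did not complete.

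The Data Analysis section states: "Pre- and post- comparisons will be made using paired, one-sample Wilcoxon signed rank tests for continuous variables". It gives no analysis set and no method for missing post values.

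Some information on withdrawn participants is collected. Up to withdrawal, the weekly calls ask about their health: "During the subsequent weekly phone calls, the exercise physiologist will inquire about any interim symptoms or events". Adverse events are reported, and withdrawals are counted and explained to the IRB at continuing review (Potential Risks/Discomforts). The later contact, about a month after completion, consists of "some additional questions via phone or mail to ascertain if they are still exercising".

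**The concern.** The withdrawal rule is triggered by a health event during the intervention under test. A link between that event and change in physical function is plausible, though not certain. Because the second assessment depends on completing the programme, following the plan as written removes these people from the pre/post comparison.

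The study has no comparison arm, so its efficacy result rests entirely on within-person change. If those withdrawn tend to worsen, the reported change belongs to participants who tolerated the exercise and may overstate benefit in those who started it. If withdrawal is unrelated to change, there is no bias and the only cost is fewer pairs.

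Two further points follow.

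- People stopped under the general sentence have an unclear status. The two sentences are compatible, but staff could keep one such person for the final measures and not another.
- Hospitalization and death are named as outcomes under Purpose and Objectives, yet their collection after withdrawal is not described. Abstraction from the medical record is a possible channel, but where the protocol describes it, neither event is named.

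**Working it through.** The plan has no figure to reproduce. The target of 20 comes from analogy with a prior study, and no effect size, SD, power or dropout rate is given. The check has two parts.

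**1. Reading the sections together**

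| Step | Source | Consequence |
|---|---|---|
| Unsafe after a session event: leaves the study | Exercise Intervention | Reason recorded; no final assessment described |
| Measures at baseline and after completion | Study measures | A withdrawn person has a baseline value only |
| Paired signed-rank test | Data Analysis | A person with one value contributes nothing |
| Missing-data rule | None found | Incomplete pairs drop out by default |

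**2. How large could the effect be?**

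From the documents: n = 20 and a 0.05 significance level (Sample Size/Data Analysis). Assumed: a two-sided test; normally distributed SPPB change with true mean 0 and SD 1.5 (range 1.0 to 2.0); one or two people lost; all losses drawn at random from the 10 with the worse change.

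*Shift in mean change.* The expected mean of the lowest 10 of 20 standard normal values is -0.767, by numerical integration of the order statistics. Removing k people from that half shifts the mean of the remaining 20 - k by

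shift = 0.767 × SD × k / (20 - k)

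- k = 1, SD 1.5: 0.767 × 1.5 × 1/19 = +0.06 points (SD 1.0 to 2.0: +0.04 to +0.08)
- k = 2, SD 1.5: 0.767 × 1.5 × 2/18 = +0.13 points (SD 1.0 to 2.0: +0.09 to +0.17)

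For scale, the standard error of the mean with 19 pairs is 1.5/√19 = 0.34, so one loss shifts the mean by 0.06/0.34, or about 0.18 of a standard error.

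*Chance of a favourable p<0.05 when there is no true change* (exact two-sided signed-rank test, simulated; only results in the direction of benefit counted):

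| Lost from worse half | Continuous change | Change rounded to whole points, with ties |
|---|---|---|
| 0 | 2.4% (exact) | 2.5% |
| 1 | about 3.5% | 3.3% |
| 2 | about 4.7% (runs gave 4.6% to 4.8%) | 4.5% |

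The rounded column is at SD 1.5, drops zeros and uses a tie-corrected normal approximation. If losses are unrelated to change, the shift is 0 and the rate stays at 2.3% to 2.6%.

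*How likely is a loss?* The documents give no rate. At an assumed 5% risk per person, the chance of at least one loss in 20 is 1 - 0.95^20 = 0.64; at 10% it is 1 - 0.90^20 = 0.88. One or two losses are 5% to 10% of the sample.

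**The case against.** The strongest reply is that the effect is small by the illustration's own figures. One loss moves the mean by under a fifth of a standard error, and even that assumes every loss comes from the worse-changing half, which nothing in the documents establishes. The plan also limits such events in advance: the exclusion criteria remove people with active angina, decompensated heart failure, known ventricular arrhythmia or continuous oxygen need, and higher-risk patients not approved for transplant at the centre must pass a submaximal exercise test. Adverse events are expected to be rare. In a pilot, a safety withdrawal is itself a finding, and it will be recorded and reported. These points stand as limits on size. They do not alter the fact that the rule, followed as written, removes people for a health-related reason from a result that will be tested at p<0.05.

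A second reply is that the fix will recover less than hoped. Study measures already lets a frailty or SPPB test be omitted if the participant or tester feels it is unsafe, and people withdrawn after an injury or emergency may be the least able to do it. This is correct. Performance measures could remain missing for informative reasons, so incomplete pairs need to be reported and explained whatever else is done.

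A third reply is that no hospitalization or death follow-up window is defined for anyone, completers included, and that those outcomes are only to be explored. That wider gap is real. The withdrawn still have a specific disadvantage: completers have weekly calls through week 8, and people who leave the study lose them.

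**Conclusion.** The concern holds. The plan withdraws from the study, rather than only from exercise, anyone judged unsafe to continue after a session event. It schedules no post-programme measures for them and uses a paired analysis that cannot include them. Bias towards benefit is possible but not certain, and its size cannot be derived from the documents.

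Under the stated assumptions, one loss, the case closest to the protocol's expectation of rare events, is a small effect. Two losses roughly double the favourable false-positive rate. This should be corrected because the remedy is cheap, not because the likely distortion is large. Confidence is medium, since the number lost and its link to outcome are assumptions.

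**What to change.** The decision on when to stop exercise stays entirely with the existing safety rules. The changes concern follow-up and analysis only.

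1. Reconcile the two sentences in Exercise Intervention so that stopping exercise is stated separately from leaving outcome follow-up. People who stop exercise remain in follow-up unless they withdraw consent.
2. At week 8, seek from them whichever study measures can safely be done, the questionnaires, and hospitalization and death status. Remote completion is already provided for: "Participants will be offered the option of completing questionnaires via Baylor College of Medicine iPAD, on paper, or over the phone".
3. In Data Analysis, define the main pre/post analysis as everyone who started and has post data, whether or not they completed the programme. Report the number of incomplete pairs for each outcome, with reasons.
4. Show the completers-only result as a sensitivity analysis.

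The cost is a wording change and one call or visit for each of the few people who stop early. The downside is a possibly less favourable result.

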English

Groups to be recruited will include:

Patients

Which if any of the following vulnerable populations will be recruited as subjects?

Vulnerable populations require special protections. How will you obtain informed consent, protect subject confidentiality, and prevent undue coercion?

Pregnant woman/fetus

Will pregnant women and/or fetuses (as described in 45 CFR 46 Subpart B) be enrolled in the research?

No

Neonates

Will neonates of uncertain viability or nonviable neonates (as described in 45 CFR 46 Subpart B) be enrolled in the research?

No

Children

Will children be enrolled in the research?

No

Design/Procedure**Design**

Select one category that most adequately describes your research:

c) Pilot

Discuss the research design including but not limited to such issues as: probability of group assignment, potential for subject to be randomized to placebo group, use of control subjects, etc.

This study is a prospective interventional study, which involves use of existing and prospectively collected data. This pilot study will be conducted at Baylor College of Medicine examining the feasibility, safety, acceptability, and preliminary efficacy of home-based exercise on frailty parameters and Short Physical Performance Battery score in patients with varying levels of kidney function. We plan to accrue up to 20 adult patients with chronic kidney disease. The effects of exercise on health-related quality of life, physical activity, and adverse outcomes including hospitalizations and death, will also be explored.

Inclusion Criteria:

1. Age 18 years or older
2. Ability to consent to research
3. Chronic kidney disease (stages 1-5)
4. A Short Physical Performance Battery score ≤ 10 and/or considered frail or pre-frail according to the Fried Frailty Phenotype

Exclusion Criteria:

1. Younger than 18 years
2. Patients being evaluated for combined organ transplantation
3. Significant comorbidities that limit rehabilitation potential including pulmonary disease requiring continuous oxygen supplementation, active angina, critical aortic sclerosis, decompensated heart failure, or known ventricular arrhythmia.
4. An Short Physical Performance Battery score >10 or not considered frail or pre-frail by the Fried Frailty Phenotype
5. Non-English speaker without availability of adequate interpreter services (safety concern)
6. Failure to pass submaximal exercise test in patients not approved for kidney transplantation at our center

Procedure

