selected walking speed will be measured using a stopwatch. To determine whether the participant is frail by the Fried Frailty Phenotype, the average of 2 trials will be calculated and adjusted for sex and height. b. Hand grip strength test: Hand grip strength will be measured using a Jamar Digital Hand Held Dynamometer. Participants will complete the grip strength test 3 times with their dominant hand (or the arm without their dialysis fistula or graft). The 3 trials will be averaged and adjusted by sex and body mass index using a normative table. c. Minnesota Leisure-time Physical Activity Questionnaire: Participants will answer questions from this questionnaire regarding how often they engage in different activities. d. Self-reported weight loss: Patients will be asked whether they unintentionally lost 10 or more pounds within the last year. e. Center for Epidemiologic Studies Depression Scale (CES-D): Participants will answer 2 questions from the CES-D about their level of exhaustion. 2. Short physical performance battery (SPPB): The Short Physical Performance Battery consists of a gait speed test over 4 meters (13.1 feet), timed repeated chair stands, and three balance tests. a. Gait speed test: The participants gait speed velocity over 4 meters will be calculated by converting the results of the participants gait speed test (please see Fried Frailty phenotype above) to meters per second. b. Timed repeated chair stands: Participants will be asked if they feel safe to stand from a chair without the use of their arms and without assistance. If the participant feels safe to stand from a chair without the use of their arms and without assistance, they will be asked to complete 5 repeated chair stands. The participants SPPB score will be determined by the time required to complete 5 repeated chair stands. c. Balance testing: The participants balance will be tested in side-by-side, semi-tandem, and tandem stands. In the side-by-side stand, participants will stand with their feet as close together as possible. In the semi-tandem stands, participants will stand with one heel touching the big toe of the opposite foot. In the tandem stands, participants will stand with the heel of one foot in front of the toes of the other foot (as if on a balance beam). Participants will be asked to hold each position for up to 10 seconds.

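### The frailty analysis variable is not named; if the frail / pre-frail class is tested by chi-square as the plan's rule implies, power in 20 patients is far below that of a paired test on the 0–5 Fried item count

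*Combined protocol and SAP*

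**What the plan says.** Under Study measures, the frailty instrument has five parts: "The Fried Frailty Phenotype consists of a gait speed test, a grip strength test, and self-reported measures of physical activity, weight loss, and exhaustion". Its overall result appears only as a class. Inclusion criterion 4 admits patients "considered frail or pre-frail according to the Fried Frailty Phenotype" (or with a low SPPB score), and the gait speed item is scored "To determine whether the participant is frail by the Fried Frailty Phenotype". No count of items met is defined, and no cut-offs for the classes are given.

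The Design section names the efficacy target as frailty parameters together with the SPPB score. It does not say whether the first means a class, a count or the separate components.

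The Data Analysis section assigns methods by variable type alone. For descriptive summaries: "Categorical variables will be summarized as counts and percentages with continuous variables summarized via medians and interquartile ranges". For tests: "Pre- and post- comparisons will be made using paired, one-sample Wilcoxon signed rank tests for continuous variables and chi-square tests for categorical variables". Then: "P-values less than 0.05 will be considered statistically significant", with no multiplicity adjustment. Frailty is not mentioned there. The form asks which comparison is primary, and the answer names none.

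The sample size is "Local: 20 Worldwide: 20", with the explanation "This is a pilot study so it doesn't require sample size calculations".

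**The concern.** Frailty is one of the two efficacy targets, yet a reader of the Data Analysis section cannot tell what will be compared before and after the programme. The one overall Fried variable that the protocol derives is categorical, so the rule as written leads to a chi-square test.

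That route loses information twice. Grouping hides changes within a class: on the usual cut-offs, a patient going from 5 items to 3 is still frail, and one going from 2 to 1 is still pre-frail. An ordinary chi-square test on the before and after counts also ignores that the same patients are measured twice. With at most 20 patients, a useful signal on overall frailty could be missed although the item data that show it are already collected.

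Leaving the variable unnamed also means that its form could be chosen after the data are seen.

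**Working it through.** **Plan's own figure.** None to reproduce: the plan gives no power, effect size or standard deviation.

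**Inputs from the documents.** N = 20, treated as all completing (the Design section says up to 20); alpha 0.05, taken as two-sided because no side is stated; five Fried items; tests by variable type.

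**Assumptions not in the documents.** Classes cut at 0, 1–2 and 3–5 items. Each item present at baseline resolves with probability 0.30; each absent item appears with probability 0.05. Three baseline distributions of 0 to 5 items:

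- mixed: .10/.25/.25/.20/.15/.05
- mostly pre-frail: .10/.35/.30/.15/.08/.02
- more frail: .05/.15/.20/.30/.20/.10

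**Step 1, implied mean change.** Mean change = −0.30 × m + 0.05 × (5 − m), where m is the mean baseline count.

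- Mixed: m = 2.20, so −0.66 + 0.14 = −0.52 items.
- Mostly pre-frail: m = 1.82, so −0.546 + 0.159 = −0.39.
- More frail: m = 2.75, so −0.825 + 0.1125 = −0.71.

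**Step 2, change hidden by grouping.** Among patients whose count changes, about 42% stay in the same class in all three mixes, or about 47% if the weight-loss item is held fixed. Over a wider set of baseline mixes and change models the share is 34–60%.

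**Step 3, simulated power** (p < 0.05 in the direction of benefit):

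| Analysis, N = 20 | Mixed | Mostly pre-frail | More frail |
|---|---|---|---|
| Chi-square on three classes (unpaired) | 5% | 3% | 16% |
| Exact signed rank on three classes | 25% | 16% | 46% |
| Exact signed rank on 0–5 count | 61% | 40% | 87% |

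**Step 4, separating the two losses.** Row 1 to row 2 is the effect of pairing (and of using the class order): 20, 13 and 30 points. Row 2 to row 3 is the effect of grouping alone: 36, 24 and 41 points. As ratios, paired class to count is 25/61 = 0.41, 16/40 = 0.40 and 46/87 = 0.53. Chi-square to count is 5/61 = 0.08, 3/40 = 0.08 and 16/87 = 0.18.

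**Step 5, dependence on how the p-value is computed.** With the normal approximation to the signed rank test, class against count is 43 against 69% (ratio 0.62), 33 against 49% (0.67) and 67 against 91% (0.74). The loss from grouping is then under half in every mix.

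**Step 6, wider assumptions.** In all, 36 cases were run: four other baseline mixes, items resolving at 0.2–0.4 and appearing at 0.05–0.1, or one-step shifts with improvement at 0.4–0.6 and worsening at 0.1–0.2. Of these, 34 gave the count at least 20% power. Among the 34:

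- chi-square on three classes had less than half the power of the count in 31;
- the exact paired test on three classes did so in 22;
- the normal-approximation paired test on three classes did so in 1.

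**Step 7, weight-loss item held fixed.** That item looks back one year and the programme lasts 8 weeks. If it cannot change, count power falls to about 48%, 30% and 78% (about 28–80% overall), and the exact paired test on three classes falls to 13%, 8% and 30%. All figures drop and the gap remains.

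**The case against.** The strongest reply is that the plan never says frailty will be analysed as a class. The class is used for eligibility and scoring, and the target is worded in the plural as parameters. A reader might infer from the summary sentence that frailty has been assigned to the categorical analysis, but that sentence concerns descriptive statistics and does not mention frailty. This stands: what the documents show is an unnamed variable plus a rule that would send the class to chi-square.

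Gait speed and grip strength are measured as continuous quantities and go to the paired Wilcoxon test. A reader might conclude that most improvement would be invisible, or that a real benefit would usually be missed. Neither follows. The two performance components are covered, and a little under half of count changes, not most, stay within a class under the main assumptions.

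It is also tempting to say that grouping by itself more than halves power. That holds in two of the three mixes with exact tests and in none with the normal approximation, and the plan does not say which it uses. Even lower power can be obtained from frail yes/no with an exact McNemar test (11%, 2% and 36%), but the protocol plans no such test. If the word paired in the test sentence was meant to cover the categorical test too, a paired categorical analysis is the nearer comparison, and row 2 above is closer to it than row 1.

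Finally, this is a pilot that claims no power, and the count has weaknesses of its own. The weight-loss item can hardly move in 8 weeks. The self-reported activity item may move simply because participants are asked to be active. These limit the gain but do not favour the class, which is built from the same items.

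**Conclusion.** The point holds in a limited form. The plan does not name its overall frailty variable; the only one it derives is a class, and its rule for categorical variables is chi-square. If that route is followed with 20 patients, power is about 3–16%, against 16–46% for an exact paired test on the same classes and 40–87% for an exact signed rank test on the item count.

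The direction is stable across the assumptions tried. The size is not: it rests on assumed class cut-offs, baseline mixes and change rates, on full follow-up of 20, and on the choice between exact and approximate p-values. Part of the shortfall is due to ignoring pairing rather than to grouping.

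This is a change that should be made, proportionate to a pilot. It is not evidence that the study cannot detect improvement in its frailty components.

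**What to change.** Add to the Data Analysis section: overall pre/post change in frailty is the change in the number of Fried items met (0–5), tested with the paired Wilcoxon signed rank test, in its exact version because ties will be common. Define how each item is scored as met, and give the class cut-offs. Report frail / pre-frail / not frail as a descriptive paired before-and-after transition table. Show the component results next to the count, so that a change driven only by the self-reported activity item can be seen.

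The cost is a few sentences, with no new data, visits or patients. There are three downsides to name. The main result is in items rather than in percent no longer frail, although the transition table still shows the latter. The one-year weight-loss item contributes little over 8 weeks and lowers power. The activity item may respond directly to the intervention.

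### Pre/post categorical comparisons are assigned plain chi-square tests, although the same participants (at most 20) are measured at both times and no matched test is named

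*Combined protocol and SAP*

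**What the plan says.** The Data Analysis section (under Sample Size/Data Analysis) gives one rule for all before/after comparisons: "Pre- and post- comparisons will be made using paired, one-sample Wilcoxon signed rank tests for continuous variables and chi-square tests for categorical variables". The next sentence deals with differences between groups and names Fisher's exact test there. The significance rule is "P-values less than 0.05 will be considered statistically significant", with no adjustment for multiple testing and no statement of sidedness.

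The data are repeated measurements on the same people. Under Study measures: "Participants will complete the following Short Physical Performance Battery testing and other study measures at baseline and after completion of the exercise program". Enrolment is capped: "We plan to accrue up to 20 adult patients with chronic kidney disease" in the Design section, and "Local: 20 Worldwide: 20" in the Sample Size section.

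The measures include categorical ones. Fried status is an entry criterion ("considered frail or pre-frail according to the Fried Frailty Phenotype") and is assessed again after the programme. One of its components is a yes/no question: "Patients will be asked whether they unintentionally lost 10 or more pounds within the last year".

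Neither McNemar's test nor any other matched test for categorical data appears in the document.

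**The concern.** In the quoted sentence, paired qualifies the one-sample Wilcoxon test; the chi-square tests carry no such qualifier. Applied literally, the rule can be carried out in two ways, and neither tests within-person change correctly.

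- **Chi-square on the before and after counts.** This treats each participant as two independent people. With positive correlation between a person's two classifications, it overstates the variance of the change. The rejection rate under no change then falls well below 5%, and power is lost.
- **Chi-square on the before-by-after cross-table.** This asks whether the earlier status predicts the later one. It can be highly significant when nothing has changed.

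Improving frailty parameters is part of the stated aim, and Fried status is a natural way to report them. With at most 20 participants there is little power to give away. The reach is limited: no categorical variable is named as primary, and gait speed, grip strength, SPPB score and actigraphy go to the paired signed-rank test.

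**Working it through.** The plan states no power or error rate for these comparisons, so there is no figure of its own to reproduce. From the document: at most 20 pairs and a 0.05 threshold (two-sided assumed). Everything else below is assumed: the shares, the within-person correlation (phi for binary items) and, for one scenario, 15 completers.

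**Why the counts chi-square is conservative.** For shares p1 and p2 measured in the same n people, the variance of the difference is [p1(1−p1) + p2(1−p2) − 2·phi·√(p1(1−p1)·p2(1−p2))]/n. The ordinary chi-square omits the last term. With no change, the true variance is (1 − phi) times what the test assumes, so the large-sample type I error is 2·[1 − Φ(1.96/√(1 − phi))]: 5.0% at phi 0, 1.9% at 0.3 and 0.6% at 0.5.

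**Worked example (assumed counts).** Frail 12/20 before and 6/20 after; six improve, none worsen.
- Counts chi-square: 40·(12·14 − 8·6)²/(20·20·18·22) = 3.64, p = 0.057 (0.112 with continuity correction).
- Exact McNemar: 2·(1/2)⁶ = 0.031. Mid-p: 0.031 − (1/2)⁶ = 0.016.

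The conclusion at 0.05 depends on the test.

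**The cross-table version.** Frail 12/20 before and 12/20 after, one person moving each way (cells 11, 1, 1, 7): 20·(11·7 − 1·1)²/(12·8·12·8) = 12.5, p = 0.0004, with no net change.

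**Binary items, 20 pairs.** All possible paired 2×2 tables were enumerated with their multinomial probabilities.

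| Test | Type I error (share 50%-60%, phi 0.2-0.6) | Power, 60% to 30% (phi 0.2-0.5) |
|---|---|---|
| Chi-square on counts | 0.2%-2.8% | 44%-46% |
| McNemar, exact | 0.4%-1.9% | 41%-56% |
| McNemar, mid-p | 1.6%-3.9% | 52%-73% |
| McNemar, asymptotic | 4.3%-4.9% | 53%-83% |

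The largest phi compatible with 60% and 30% is (0.30 − 0.18)/√(0.24·0.21) = 0.53. Exact McNemar is below the chi-square at phi 0.2-0.3. With 15 completers, power is 32%-36% for the chi-square and 38%-47% for mid-p.

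The advantage needs positive correlation. At phi 0 with 20 pairs, the chi-square has 46% power and mid-p 44%. Repeat classifications of the same person 8 weeks apart should be positively correlated.

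**Three-level Fried status, 20 pairs.** This was simulated from a latent bivariate normal with correlation 0.3, 0.5 and 0.7, which gives a correlation of the categories of 0.23 to 0.55. There were 20,000 data sets per scenario (5,000 for the Stuart-Maxwell figures below). The assumed shift in not frail/pre-frail/frail is from 5/45/50% to 25/50/25%.
- Power: 2×3 chi-square 40%-43%; signed-rank on the ordered category 63%-85% (54%-76% with exact p-values).
- Type I error with no change (10/50/40%): chi-square 0.7%-2.7%; signed-rank 4.1%-4.5% (exact 1.7%-2.2%).

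That gain has two parts. A matched test that ignores order (Stuart-Maxwell) has power of about 47%, 56% and 69% at latent correlation 0.3, 0.5 and 0.7, against 43%, 42% and 40% for the unpaired chi-square. Pairing alone is therefore worth about 4, 14 and 29 points. The rest, up to about 64%, 72% and 84% in the same comparison, comes from using the order.

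**The case against.** The strongest reply is that the authors meant a matched chi-square. The sentence opens by announcing before/after comparisons, paired comes early in it, and a different categorical test is reserved for between-group differences. McNemar's test is a chi-square-type test, and matched extensions exist for three categories (Stuart-Maxwell, McNemar-Bowker). This may well be the intent, and asymptotic McNemar would be valid for binary items. But the text does not say so, McNemar's own test does not cover three levels, and an analyst who follows the sentence as written would run the unpaired test.

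Other points stand as limits on size:
- Much of the three-level gain comes from ordering, and at low correlation most of it does.
- The binary gain is small at low correlation: about 6 points at phi 0.2 with 20 pairs and 2 points with 15.
- Exact McNemar is not a dependable improvement; with 15 pairs it is below the chi-square at every phi examined (25%-28% against 32%-36%).
- Asymptotic McNemar also holds its level in these scenarios and has more power than mid-p, so the choice between those two is a judgement.
- The weight-loss item is a weak example. It looks back over a year and the programme lasts 8 weeks, so the two windows largely overlap and any test would see little change.
- This is a pilot, and its numeric outcomes are tested properly. Even so, the plan applies a 0.05 threshold to its comparisons, so the test should fit the data.

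**Conclusion.** The concern holds. The test assigned to before/after categorical variables does not match the paired design as written, and no matched test is named elsewhere. If applied to the before and after counts, it would tend to miss a real change in frailty status and, with positive within-person correlation, would not inflate false positives. If applied to the cross-table, it would answer a different question.

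Under the assumed scenarios with 20 pairs, the loss against mid-p McNemar is roughly 6 to 29 percentage points of power for a binary status (46% against 52% at phi 0.2; 44% against 73% at phi 0.5). For three-level Fried status it is larger, but pairing accounts for only part of it. These sizes depend on shares and correlations that the document does not give; the mismatch itself does not. It should be fixed, but it does not threaten the numeric outcomes.

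**What to change.** In the before/after sentence of the Data Analysis section, replace the chi-square tests for categorical variables with: *McNemar's test (mid-p version) for binary variables, and the Wilcoxon signed-rank test on the ordered Fried category (not frail, pre-frail, frail)*. Add that these tests use participants with both measurements. If McNemar's chi-square was intended, naming it settles the binary items, but the three-level status still needs its own matched test. State whether signed-rank p-values for the Fried category will be exact or asymptotic with tie correction, because the two differ noticeably at this size.

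The cost is a short text change made before analysis. No new data, visits or participants are needed.
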